## 7.0 Trial Evaluations

#### 7.1. Accuracy and Reproducibility

Standard methods to calculate random and systematic errors will be used(33) taken from ontreatment imaging on days 1-3, then weekly until treatment completion. The random and systematic errors analysis will be reported with confidence intervals to allow estimation of the effect size for random and systematic errors (the probable primary endpoint for the definitive study) to check that the likely effect is within a clinically relevant range (as confirmation that it is worth progressing with the full trial). To check positioning patients in both arms of the study will have a single image taken at the start of the daily treatment exposure. This image will be used to confirm set up accuracy before the treated dose is delivered.

#### 7.2 Plan acceptability

Patients randomised to receive the intervention (the S4A bra) will have two CT planning scans (one with and one without the S4A bra). Each scan will be planned as normal but patients will only be treated using the plan with the patient wearing the S4A bra. Both scans will be compared using the following parameters:

- Time taken to achieve an acceptable plan
- Beam energy required to achieve an acceptable plan
- Comparison of dose volume histograms for Planning Target Volume (PTV), lungs and heart (for women planned for a left sided breast cancer).
- Dose to organs at risk, lungs and heart mean doses (see section 7.5 for specific dose measurements to be recorded).

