#### 4.0 Trial Design

The SuPPORT 4 All (S4A) study is a single centre randomised feasibility trial. The safety of the product in terms of the radiation absorption properties have been fully tested through a series of physics tests performed on both a 6 and 10MV linear accelerators (see Appendix 1). The positional accuracy achievable using the S4A bra has been tested through a Healthy Volunteer Study using 3D surface scanning (stereophotogrammetry). Hence the purpose of this feasibility trial is to test the acceptability of the SuPPORT 4 All bra by patients (in terms of comfort, modesty and usability) and staff (in terms of ease of daily set-up) and to assess the appropriateness of a range of measurement tools that might be used in post implementation surveillance as part of the on-going update to the product technical file.

This study also proposes to assess the impact of the bra on the ability or ease of producing an acceptable radiation treatment plan. To achieve this those patients randomised to the intervention arm will undergo two planning CT scans (using a repeated measures design); one CT scan while

wearing the S4A bra and one scan as normal without the bra. Thus enabling a direct comparison between participants of dose homogeneity achievable with and without the bra.

The following parameters are standard tools or measures that will be adopted in the study (see section 7.0 for more details) some are validated tools others are being tested for the first time in this study:

- Skin reactions using a standard measuring tool Radiation Therapy and Oncology Group skin scoring assessment (RTOG)(1).
- Incidence of moist desquamation in the inframammary fold.
- Dose to organs at risk (mean lung and mean heart doses) taken from the patient's individual dosimetry plan (see section 7 for further details).
- Patient comfort measured via a new comfort questionnaires designed specifically for this study.
- Patient modesty measured by aspects of the patient modesty scale(2) within a newly developed story board of the radiotherapy journey to measure patient experiences.
- Patient empowerment using the 15-item patient empowerment scale for cancer patients(32)
- Technology acceptance from both healthcare practitioners and patients using an adapted Technology Acceptance Tool (based on the Technology Acceptance Model(4)).
- Body Image using the 10-item body image scale(5)

[figure not shown]

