# Table 2 The Research Questions and the associated outcome measures proposed for this feasibility trial.

No	Research question	Proposed Assessment Method
1	Is the design and current functionality of the bra able to fit with current set-up procedures without too much process adaptation?	Interview of staff involved in the planning and treatment of patients using the bra.
2	Does the bra make it easier to produce an acceptable treatment plan?	Those in the intervention arm will undergo two planning CT scans one with and one without the S4A bra. Two radiotherapy treatment plans will be produced for each patient in the intervention arm; the patient will only be treated using the plan with the patient wearing the S4A bra. Plan evaluations will include measures of dose homogeneity across the planning target volume, time taken to plan, complexity of plan and beam energy required to produce the optimal plan.
3	What are the random and systematic errors in breast positioning with the immobilisation support bra compared with a control group with standard immobilisation (no bra)?	Accuracy derived from on-treatment images on days 1-3 and weekly until the end of treatment for five different parameters (see section 12.1).
4	Is accuracy of positioning using the support bra the same across all breast sizes?	Using individual mean random and systematic errors to correlate with breast volume taken from the radiotherapy plan.
5	What are the differences in the dose to organs at risk when the support bra is used compared with no support bra?	Mean lung and mean heart dose compared between bra and no bra cohorts.
6	Does the support bra reduce the	Skin assessments by health care

	incidence of dry/moist desquamation in the inframmary fold	practitioners taken at baseline and weekly during treatment with comments on the skin scoring (using RTOG) in the inframmary fold ie dry/moist desquamation yes/no and duration
7	Is the current inflation bra design appropriate for patients' aesthetic, and comfort needs?	Assessed with comfort assessment tool (using questions derived from Healthy Volunteer study questionnaire analysis and interviews).

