#### **10.7 Radiotherapy Planning Data**

Dose-volume histograms (DVHs) are generated for the PTV, ipsilateral lung and heart.

The parameters in Table 6 below should be recorded.

The parameters used to produce the optimum plan will be recorded for each participant (and for each plan produced comparing S4A bra and no bra scans for those women randomised to the intervention arm).

Table 6 Radiotherapy Planning data Recorded for each Patient.

	Structure	Parameter		
Radiotherapy to left or right	PTV	Maximum point dose		
breast		V42.8 Gy		
		V 42 Gy		
		V 38 Gy		
	Ipsilateral lung	V 12 Gy		
		Mean dose		
	Combined lungs	Total combined mean lung dose		
Radiotherapy to left breast only	Heart	V 10Gy		
		V 2Gy		
		Mean dose		
Planning information				
Beam energy required				
Number of fields required				
Time to achieve acceptable plan				
Ease/difficulty of planning score (1 to 3)	2=standard, 1=easier & 3=more difficult			

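### The paired bra/no-bra planning comparison neither balances nor records planning order or planner, so its time and ease results could mix the bra's effect with order

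*Protocol*

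**What the plan says.** Section 4.0 states that "those patients randomised to the intervention arm will undergo two planning CT scans (using a repeated measures design"), one with and one without the bra, and gives the purpose as follows: "Thus enabling a direct comparison between participants of dose homogeneity achievable with and without the bra". Section 7.2 adds: "Each scan will be planned as normal but patients will only be treated using the plan with the patient wearing the S4A bra". The first parameter it lists for comparison is "Time taken to achieve an acceptable plan", followed by beam energy, dose-volume histograms and organ doses.

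Table 2, question 2 asks "Does the bra make it easier to produce an acceptable treatment plan" and answers it from this paired design: "Plan evaluations will include measures of dose homogeneity across the planning target volume, time taken to plan, complexity of plan and beam energy required". Table 6 in section 10.7 records, for each participant and for each of the two plans in the bra arm, "Time to achieve acceptable plan" and an ease score in which 1 is easier, 2 standard and 3 more difficult. The Trial Summary lists ease of planning with the bra compared with no bra among the secondary feasibility endpoints.

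The protocol does not fix or balance the order in which the two plans are made. It does not say whether one person makes both, or whether the person scoring ease is unaware of the condition. Masking is stated only for the RTOG skin scores (section 7.3). Table 6 has no entry for planning order or planner.

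**The concern.** Planning the same woman twice is a two-period comparison. Whoever makes the second plan may already know her anatomy, contours and workable beam arrangement from the first. If most women have their plans made in the same order, this familiarity acts in one direction in every pair, and more patients do not average it out. Planning time and the ease score are the most exposed, because both measure the planner's work directly.

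A second possible bias is unequal effort, since one plan will treat a patient and the other will not.

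At stake is the interpretation of Table 2, question 2 and of one secondary feasibility endpoint. The second CT scan is introduced for this comparison and carries a stated 7.2 mSv and an additional cancer risk of 0.04% (section 21.0), which is a further reason to make the comparison readable. A later analysis plan cannot repair the gap: order has to be set before the plans are made, and it cannot be adjusted for if it is not recorded.

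**Working it through.** **Number of pairs.** Section 5.2 needs 40 evaluable patients and allows 20% attrition: 40 / (1 − 0.20) = 50, or 25 per group. This reproduces the protocol's figure. It gives 25 bra/no-bra pairs, or 20 if attrition reaches 20% before both plans exist. The protocol states no precision for the planning comparison itself.

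**Bias in the paired difference.** Let *c* be the change in the second plan due to order alone, and *f* the share of women whose bra plan is made second. The bias in the mean difference (bra minus no bra) is (2*f* − 1)*c*.

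- Bra first for all (*f* = 0): bias = −*c*. If the second plan is quicker (*c* negative), the bra looks slower.
- Bra second for all (*f* = 1): bias = +*c*.
- 75/25 split: bias is half of *c* in size.
- Balanced, 13 and 12 of 25: (2 × 13/25 − 1)*c* = 0.04*c*, effectively zero. Allowing for order in the analysis removes the rest.

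**Consequence for the confidence interval.** *c* is not in the protocol, so a range of 0.25 to 0.75 SD of the paired difference is assumed. The table gives the probability that a paired-t 95% interval excludes zero when the bra has no effect (noncentral t with n − 1 degrees of freedom and noncentrality bias × √n). The interval half-width is 0.468 SD with 20 pairs and 0.413 SD with 25.

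| Order | Pairs | c = 0.25 | c = 0.50 | c = 0.75 |
|---|---|---|---|---|
| Uniform | 20 | 18.6% | 56.5% | 88.9% |
| Uniform | 25 | 22.5% | 67.0% | 94.9% |
| 75/25 | 20 | 8.3% | 18.6% | 35.7% |
| 75/25 | 25 | 9.2% | 22.5% | 43.6% |
| Balanced | 20 or 25 | 5% | 5% | 5% |

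On the time scale, if familiarity made the second plan 10% to 30% quicker (also an assumption), a uniform order would shift the mean difference by that 10% to 30%, and a 75/25 split by 5% to 15%.

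**What the between-arm data can add.** Table 6 also covers control women, whose no-bra plans are delivered and have no earlier plan behind them. A between-arm comparison of time therefore has bias *f* × *c*, from bra plans made second. It is zero among women whose bra plan was made first, and 0.5*c* over all bra women under balanced order. Order must be recorded to use this comparison properly.

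**What limits unequal effort.** Both plans are to be planned as normal under the single set of rules in section 10, with the limits in Tables 4 and 5. Those tables give both mandatory and optimal values for some parameters, and section 7.2 does not say which level makes a plan acceptable. The second physics check in section 13.0 refers to the treatment plan of the first ten cases and does not name the undelivered one.

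**The case against.** The strongest reply is that the protocol is silent on order and does not prescribe a bad one. That stands. A reader might infer that the bra plan is always made first because it is needed for treatment, but no text says so. Even on scan order the only hints differ: section 21.0 lists the bra scan first, while section 9.2.1 lets the patient go home in the bra after the planning scan. If order varies in practice the bias shrinks, and carry-over needs a shared planner or reused work, which is also not stated.

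A reader might also infer that the undelivered plan gets less effort. Both plans fall under the same rules and limits, so this is possible but not shown. The ease score is anchored to standard practice and is not worded as a rating against the woman's other plan, which weakens the order effect on it somewhat.

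It is also fair to say that question 2 does not rest on the pairs alone in terms of available data. Table 6 and section 16.0 give planning time in both arms, Table 2 question 5 compares organ doses between cohorts, and the lung and heart criteria in Table 1 are set against the control arm. No stop/go criterion uses the paired comparison, and section 17.0 describes the analysis as mainly descriptive.

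What remains is that the stated method for question 2 is the paired one, its order is uncontrolled and unrecorded, and a descriptive confidence interval is displaced by order just as a test would be.

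**Conclusion.** The point holds as a cheap design improvement. Paired planning time and ease may be confounded with planning order because order and planner are neither balanced nor recorded. The bias runs from zero, if order happens to be balanced or nothing carries over, to the whole order effect, if order is uniform. At an assumed effect of 0.5 SD and uniform order, the interval would wrongly exclude zero in 57% (20 pairs) to 67% (25 pairs) of trials. These figures rest on an order effect that the protocol does not give.

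The documents do not support the stronger readings that a bra-first order is built in, that the no-bra plan is worked up less, or that question 2 cannot be answered at all. Nor do they give a reason to alternate the scan order. Organ doses are less exposed, and progression to the definitive trial does not turn on this comparison.

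**What to change.** In section 7.2:

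- Allocate planning order from a pre-made balanced list, half with the bra plan first and half with the no-bra plan first.
- Apply the same acceptance check to both plans, stating what counts as acceptable. Balancing order does not deal with unequal effort; this does.
- Report the paired time and ease results allowing for order.
- Report the between-arm planning time and ease beside them, showing separately the women whose bra plan was made first.

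In Table 6, add planning order and planner for each plan. In section 4.0, change the description of the comparison from between to within participants. The scan order can stay as it is.

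Both plans are already being made, so the cost is a short list, two data items and some wording. The drawback is that about 12 women (half of 25) would have their treatment plan finished second, which has to fit within the usual planning time.

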#### 7.3. Skin Toxicity

Skin toxicity will be measured using validated skin assessment scoring systems as follows:

• The Radiation Therapy Oncology Group (RTOG) toxicity scoring scale for acute skin reactions(1).

• A lay RTOG scoring system for patient self reporting (developed within the co-design workshops with patients and healthcare practitioners). This tool has not been validated and ease of use and comparison of lay scoring with HCP scoring will be assessed within this study.

RTOG scores will be recorded at day 0 (at the CT planning visit) and once weekly until the end of treatment by a designated radiographer blind to the intervention group and self reported by the patient. The patient will also self-report skin reactions at four weeks post treatment. In addition, participants will be asked to complete a breast assessment, the SELF tool (SizE, Look, Feel), designed for patients to monitor and document breast swelling that maybe indicative of breast oedema. User representatives and healthcare practitioners designed both these patient self-scoring tools in the product development phase of this study. The aim of introducing these tools in this feasibility study is to assess compliance, usefulness and ability for patients to score skin and breast changes themselves; constituting the first part of the validation process for these tools.

## 7.4. Patient comfort, Modesty, Empowerment

#### 7.4.1. Assessing patient comfort

In order to assess patient comfort with and without the support bra a new comfort questionnaire has been designed based on interviews with healthy volunteers that have worn the support bra. Patients will be asked to complete the questionnaire after the first treatment session and once weekly until the end of the treatment course. As the patients' skin may become sore as treatment progresses it is important to ensure the support bra does not exacerbate skin discomfort.

#### 7.4.2. Assessing patient modesty

A story-board documenting the radiotherapy journey has been developed to enable participants to define experiences of being naked and un-covered at different points in the radiotherapy pathway.

## 7.4.3. Assessing patient empowerment

Patients will be asked to complete the 15-item patient empowerment scale for cancer patients (32) at day 0 (Radiotherapy planning CT visit) and once weekly during treatment (ie week 1, week 2 and week 3).

## 7.5. Dose to Organs at Risk

Dose to organs at risk will be assessed at the planning stage for all trial patients the following parameters will be calculated for all patients:

- Mean ipsilateral lung dose
- V12- Volume of ipsilateral lung receiving more than 12Gy total dose.
- Combined lungs total mean lung dose.

For patients undergoing radiotherapy to the left breast the following additional parameters will be calculated:

- Mean heart dose
- Percentage of heart volume receiving >10Gy and 2Gy

<sup>1 The Patient RTOG and SELF tool can be found in the supplementary files

# Table 2 The Research Questions and the associated outcome measures proposed for this feasibility trial.

No	Research question	Proposed Assessment Method
1	Is the design and current functionality of the bra able to fit with current set-up procedures without too much process adaptation?	Interview of staff involved in the planning and treatment of patients using the bra.
2	Does the bra make it easier to produce an acceptable treatment plan?	Those in the intervention arm will undergo two planning CT scans one with and one without the S4A bra. Two radiotherapy treatment plans will be produced for each patient in the intervention arm; the patient will only be treated using the plan with the patient wearing the S4A bra. Plan evaluations will include measures of dose homogeneity across the planning target volume, time taken to plan, complexity of plan and beam energy required to produce the optimal plan.
3	What are the random and systematic errors in breast positioning with the immobilisation support bra compared with a control group with standard immobilisation (no bra)?	Accuracy derived from on-treatment images on days 1-3 and weekly until the end of treatment for five different parameters (see section 12.1).
4	Is accuracy of positioning using the support bra the same across all breast sizes?	Using individual mean random and systematic errors to correlate with breast volume taken from the radiotherapy plan.
5	What are the differences in the dose to organs at risk when the support bra is used compared with no support bra?	Mean lung and mean heart dose compared between bra and no bra cohorts.
6	Does the support bra reduce the	Skin assessments by health care

	incidence of dry/moist desquamation in the inframmary fold	practitioners taken at baseline and weekly during treatment with comments on the skin scoring (using RTOG) in the inframmary fold ie dry/moist desquamation yes/no and duration
7	Is the current inflation bra design appropriate for patients' aesthetic, and comfort needs?	Assessed with comfort assessment tool (using questions derived from Healthy Volunteer study questionnaire analysis and interviews).
8	Does the support bra provide measureable changes in patient modesty?	Modesty assessed with the Storyboard of the process with and without the bra – participants asked to choose responses that represent their experiences of physical exposure measured after day 1 and repeated in the final week of treatment. Patients in the control arm are given the storyboard without the bra and asked to rate their experience; patients in the intervention arm given the storyboard with the bra and asked to rate their experience. In the final week of treatment participants are given both storyboards and asked to choose their preference.
9	Does the support bra allow measurable changes in feelings of empowerment compared with the standard no immobilisation process?	Measured using the 15-item patient empowerment scale for cancer patients.
10	Are there any treatment related cost savings from using the support bra?	
 
Assessed through the recording of:
 
1. Time taken for the CT radiotherapy planning session.
 
2. Time taken for the radiotherapy dosimetry planning.
 
3. Time taken for each treatment session.
 
4. The number of extra/repeated ontreatment imaging exposures.
 
5. The number of repeat plans required.
 
6. A measure of the grades of staff required undertaking CT planning, dosimetry planning and treatment set-up procedures.
 

11	Are the patient self-reporting tools easy to use and complete?	Compliance with completion, number of correctly completed booklets and comments made in the booklet by patients.

12	Do HCP RTOG scores correlate with the patient-self reporting scores?	Comparison of HCP recorded RTOG scales and patient scores recorded in the patient- held booklet.
----	--	--

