In addition, an ancillary patient self-reporting booklet will be used and this contains:

- Sections to record the size of the bra and all the fitting dimensions (strap positions and details about fit) for those in the intervention arm.
- A self-reporting skin scoring scale based on the RTOG system and
- A tool for measuring and monitoring changes in the breast the SELF tool (SizE, Look, Feel).

The self-reporting tools will also be assessed for acceptability and usability in this feasibility study. The purpose of the patient self-reporting booklets is to enhance patient input to their own treatment, provide some opportunity for patient control and for empowerment. To aid this a comparison of patient self-reporting of skin reactions will be assessed against reporting by the healthcare practitioners to measure comparability.

Figure 1. Trial Flow Diagram

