## 8.0 Radiotherapy

#### 8.1. Dose prescription

The dose prescription is 40 Gy in 15 fractions; treating each field daily. The dose is prescribed to the reference point to which the dose distribution is normalised.

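### Table 2 question 12 asks whether staff and patient skin scores correlate, but the stated purpose, comparability of a lay version of the same scale, calls for agreement

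*Protocol*

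**What the plan says.** Table 2, question 12 of the protocol asks "Do HCP RTOG scores correlate with the patient-self reporting scores". The method column beside it reads "Comparison of HCP recorded RTOG scales and patient scores recorded in the" patient-held booklet, and names no statistic.

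The purpose is given elsewhere. Section 4.0 says that "a comparison of patient self-reporting of skin reactions will be assessed against reporting by the healthcare practitioners to measure comparability". Section 7.3 says of the lay scale: "This tool has not been validated and ease of use and comparison of lay scoring with HCP scoring will be assessed within this study". It describes the work on the self-scoring tools as "constituting the first part of the validation process for these tools".

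On timing, section 7.3 states: "RTOG scores will be recorded at day 0 (at the CT planning visit) and once weekly until the end of treatment", by a radiographer blind to group and by the patient herself. The patient alone scores again four weeks after treatment. Section 3.1.3 lists the lay score among the measures whose suitability for the main trial is to be evaluated.

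Section 17.2 covers RTOG summaries by arm and the difference between arms. It does not mention the comparison of patient with staff.

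**The concern.** The lay scale is based on the RTOG system, so its grades are meant to carry the same meaning. What a validation step needs to know is whether a patient's grade 2 is also a staff grade 2. A correlation coefficient does not answer that, because it is unchanged when one rater is shifted by a constant.

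One grade matters on this scale. Section 5.2 treats a score of 3 or more, on a scale of 0 to 4, as a negative event. After treatment ends, the patient's own score is the only planned skin score. An analyst who answers question 12 as written could report a favourable result for a tool that misgrades by a full category, and that result would feed the judgement on the tool's suitability for the main trial.

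**Working it through.** **No figure to reproduce.** The protocol gives no sample size, target coefficient or tolerated grade difference for this comparison. What can be checked is what the question, taken literally, can and cannot detect. The protocol gives no grade distributions, so those used below are assumptions.

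**Question against purpose.** Section 4.0 wants comparability. Section 7.3 wants a first step in validating a lay version of the same ordinal grades. Both concern agreement between two raters on one scale. Question 12 asks about association. No section names an agreement measure.

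**Check 1: constant offset.** Let *s* be the staff grade and *p* = *s* + 1 the patient grade.

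- Pearson correlation = Cov(*s*, *s* + 1) / [SD(*s*) × SD(*s* + 1)] = Var(*s*) / Var(*s*) = 1.00. The ranks are unchanged, so Spearman is also 1.00.
- Exact agreement = 0%.

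These two results hold for any distribution in which staff grades vary. The rest needs an assumed distribution. Take 40 patients (the evaluable number in section 5.2) with staff grades 0/1/2/3 in 4/24/11/1 patients:

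- Unweighted kappa: chance agreement = (24×4 + 11×24 + 1×11) / 40² = 371/1600 = 0.232; kappa = (0 − 0.232) / (1 − 0.232) = −0.30.
- Quadratic-weighted kappa: the staff mean is 49/40 = 1.225 and the variance is 77/40 − 1.225² = 0.424. The observed mean squared difference is 1. The difference expected by chance is 2 × 0.424 + 1² = 1.849. Kappa = 1 − 1/1.849 = 0.46.
- Linear-weighted kappa: 1 − 1/1.095 = 0.09.
- Grade 3 or more: 1 of 40 by staff, 11 + 1 = 12 of 40 by patients.

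**Check 2: shared rise over weeks, if visits were pooled.** Section 8.1 states: "The dose prescription is 40 Gy in 15 fractions". Section 11.0 gives them daily from Monday to Friday, which is three weeks, so there are four paired scores per patient including day 0. Staff and patient grades were simulated for 40 patients as independent of each other within each visit, over 800 simulated trials per set. Assumed percentages at grades 0/1/2/3:

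| Set | Day 0 | Week 1 | Week 2 | Week 3 |
|---|---|---|---|---|
| Flat | 90/10/0/0 | 70/28/2/0 | 50/42/8/0 | 30/50/19/1 |
| Middle | 97/3/0/0 | 60/38/2/0 | 20/65/14/1 | 5/60/32/3 |
| Steep | 100/0/0/0 | 50/50/0/0 | 10/70/20/0 | 0/45/50/5 |

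| Mean result | Flat | Middle | Steep |
|---|---|---|---|
| Spearman, four visits pooled | 0.23 | 0.53 | 0.66 |
| Quadratic-weighted kappa, four visits pooled | 0.22 | 0.48 | 0.62 |
| Spearman within week, weeks 1–3 | 0.00 | 0.00 | 0.00 |
| Unweighted kappa within week, weeks 1–3 | 0.00 | 0.00 | 0.00 |

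Pooling inflates weighted kappa about as much as it inflates the correlation. Changing the statistic is therefore not enough; the summary has to be made visit by visit.

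**Check 3: agreement within one grade.** In week 3 of the middle set, with independent scores, the chance of differing by two or more grades is 2 × (0.05×0.32 + 0.05×0.03 + 0.60×0.03) = 0.071. Agreement within one grade is then about 93%, although the patient's score carries no information. Exact agreement by chance is 0.05² + 0.60² + 0.32² + 0.03² = 0.466, or 47%. Agreement within one grade is thus close to its ceiling and cannot stand alone.

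**The case against.** The strongest reply is that the protocol does not commit to a correlation. The word appears only in the question. The method column and sections 4.0 and 7.3 all speak of comparison or comparability. Where Table 2 does intend a correlation, in question 4 on breast volume, it says so in the method column. The choice of statistic is commonly left to a statistical analysis plan, which is not at hand. This stands, and it limits the point to the framing of the question. It does not remove it: an analysis plan that follows question 12 literally would inherit a question that does not match the purpose.

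Three stronger readings are tempting, and the protocol does not support them.

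- A reader might infer that the lay tool will be judged by a significance test that it would almost always pass. Section 17.0 describes the analysis as mainly descriptive and based on confidence intervals, and no such test is mentioned.
- A reader might infer that the weekly rise will inflate the result. That requires pooling over visits, which is nowhere stated, so Check 2 shows only what pooling would do.
- A reader might infer that question 12 decides whether the tool goes forward. Table 1 has no criterion on patient–staff scores, and nothing says that the lay score feeds the grade 3 criterion. The only stated route to dropping a questionnaire is excess missing data (section 3.1.4). The result informs suitability and no more.

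**Conclusion.** The point holds as a mismatch between question 12 and the purpose given in sections 4.0 and 7.3. Taken literally, the question cannot detect a systematic offset: a constant one-grade shift gives a correlation of 1.00 with 0% exact agreement, assuming only that staff grades vary. The kappa values and the 1 against 12 patients at grade 3 or more depend on one assumed distribution. The pooled correlations of 0.23 to 0.66 depend on assumed distributions and on pooling, which the protocol leaves open.

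The point is minor. It concerns a secondary tool-validation question and leaves the primary feasibility outcome, the sample size, the stop/go criteria and the data collection untouched.

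**What to change.** Reword question 12 as: *Do patient self-reported scores agree with HCP RTOG scores?* In its method column, state that the following will be reported separately for each visit at which both are scored:

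- the cross-table of patient against staff grade;
- the percentage in exact agreement;
- weighted kappa with 95% CI;
- the direction and size of disagreement (patient minus staff), including at grade 3 or more.

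Do not make an estimate pooled over weeks the main summary. Clustered or bootstrap intervals change the width of the interval but do not remove the inflation from the shared weekly rise. Do not rely on within-one-grade agreement alone.

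The cost is a change of wording and slightly more tabulation of scores that are already collected. Kappa will be unstable or undefined at visits where nearly all scores are the same, as may happen at day 0; there the cross-table and exact agreement must carry the result.
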